5.1.1 Data Collection

Location of data storage

The majority of the research data will be entered directly into a data management software program (REDCap), using either an on-site computer or an iPad on the Yale secure network. Paper collection materials (such as parts of the MoCA) will be scanned into REDCap and then stored in locked file cabinets. Data coordination, data management and database design will occur within the Yale School of Medicine's Program on Aging (POA). All data will be collected and maintained electronically. Data management procedures will ensure accurate and efficient data collection and analysis; confidentiality and real-time, on-demand study monitoring reports. Patient identifiers will be collected to facilitate gathering of complete data from the electronic medical record (EMR), but all participants will be assigned a unique REDCap study ID for identification in the study. Data will be maintained in accordance with HIPAA guidelines for participant confidentiality and privacy. All data will reside on secure, HIPAA-compliant database and file-sharing resources managed by the Data Management and Informatics Core (DMIC) of the POA and by Yale ITS. Access to data resources will be strictly limited to research staff and investigators.

Data collection and data elements

The data elements and method of collection during the study visits and for the EMR abstraction are outlined above in Section 5.1; therefore, in this section we will add these details for data elements related to the primary outcomes. To evaluate the feasibility of bundle delivery in the ICU (SA1), we will assess the delivery of each bundle component separately. For the occupational therapy intervention (*Component 1*), we will review the electronic medical record (EMR) for OT notes/flowsheet data from study enrollment through hospital discharge. In addition to gathering data on numbers of patients receiving OT, we will gather data about the frequency of and which OT interventions are performed. For the hearing impairment intervention (*Component 2*), we will sum data from the daily audit. Of note, if the patient is deeply sedated or unconscious due to critical illness, that day would not count as an eligible day of hearing amplifier use. For the deprescribing intervention (*Component 3*), we will review the chart for the ICU pharmacist's note. We will also gather data on the details of the deprescribing intervention (i.e. the number and type of medications that were changed or discontinued) as preliminary data for future studies.

To evaluate the acceptability of the geriatrics bundle among providers who are responsible for delivering and using the individual components (occupational therapists, nurses, physicians, and ICU pharmacists), we will administer a survey with a 5-point Likert scale (range 1-5, where 5 indicates that the bundle is completely acceptable for use in its current form) to the providers who are responsible for

delivering the intervention: occupational therapists (OT; *Component 1*), nurses (primarily, but also other ICU providers such as physicians and physical therapists; *Component 2*), and ICU pharmacists (*Component 3*). The survey will include questions about whether the device improved workflow (e.g. For PT, did it help facilitate early mobilization?) and ask for feedback that may help adapt the intervention to improve its utility. For the deprescribing component, we will administer the survey to the ICU pharmacist after they have performed the intervention. The acceptability survey will be developed during the study to allow the investigator team to observe implementation of the geriatrics bundle and ensure that the survey is assessing all important workflow elements.


5.1.2 Adverse Events Definition and Reporting

a. Attribution of Adverse Events:

Adverse events will be monitored for each subject participating in the study and attributed to the study procedures / design by the principal investigator ([name]) according to the following categories:

- a.) Definite: Adverse event is clearly related to investigational procedures(s)/agent(s).
- b.) Probable: Adverse event is likely related to investigational procedures(s)/agent(s).
- c.) Possible: Adverse event may be related to investigational procedures(s)/agent(s).

- d.) Unlikely: Adverse event is likely not to be related to the investigational procedures(s)/agent(s).
- e.) Unrelated: Adverse event is clearly not related to investigational procedures(s)/agent(s).

b. Plan for Grading Adverse Events:

The following scale will be used in grading the severity of adverse events:

1. Mild adverse event
2. Moderate adverse event
3. Severe

c. Plan for Determining Seriousness of Adverse Events:**Serious Adverse Events:**

In addition to grading the adverse event, the PI will determine whether the adverse event meets the criteria for a Serious Adverse Event (SAE). An adverse event is considered serious if it results in any of the following outcomes:

1. Death;
2. A life-threatening experience in-patient hospitalization or prolongation of existing hospitalization;
3. A persistent or significant disability or incapacity;
4. A congenital anomaly or birth defect; OR
5. Any other adverse event that, based upon appropriate medical judgment, may jeopardize the subject's health and may require medical or surgical intervention to prevent one of the other outcomes listed in this definition.

An adverse event may be graded as severe but still not meet the criteria for a Serious Adverse Event. Similarly, an adverse event may be graded as moderate but still meet the criteria for an SAE. It is important for the PI to consider the grade of the event as well as its "seriousness" when determining whether reporting to the IRB is necessary.

d. Plan for reporting UPIRSOs (including Adverse Events) to the IRB

The principal investigator will report the following types of events to the IRB:

Any incident, experience or outcome that meets ALL 3 of the following criteria:

Is unexpected (in terms of nature, specificity, severity, or frequency) given (a) the research procedures described in the protocol-related documents, such as the IRB-approved protocol and informed consent document and (b) the characteristics of the subject population being studied; AND

Is related or possibly related to participation in the research (*possibly related* means there is a reasonable possibility that the incident, experience, or outcome may have been caused by the procedures involved in the research); AND

Suggests that the research places subjects or others at greater risk of harm (including physical, psychological, economic, legal, or social harm) than was previously known or recognized.

Unanticipated Problems Involving Risks to Subjects or Others (UPIRSOs) may be medical or non-medical in nature, and include – but are not limited to – *serious, unexpected, and*

related adverse events and unanticipated adverse device effects. **Please note** that adverse events are reportable to the IRB as UPIRSOs **only** if they meet all 3 criteria listed above.

5.2 Study Schedule

All patient participants will have two 45-minute study visits that include assessments by the research team. The first visit will occur in the ICU and the second will occur on the hospital ward, prior to hospital discharge. All patient participants will also receive a brief follow-up phone call at approximately 30 days after hospital discharge. For participants in the intervention arm, study personnel will also perform a daily 5-minute audit of hearing amplifier device use and gather data about acceptability from the participant and nurse (when available).

The study schedule for provider participants will include a brief survey (5-10 minutes), and, for the subset that agree to participate in focus groups, one additional study visit for the focus group (lasting approximately 1 hour on a separate date).

5.3 Informed Consent

For patient participation in the study, we will obtain informed consent. The patient and/or their proxy will be approached in the ICU by study personnel. All patient rooms in the ICU are private rooms. The patient's ability to make an informed decision will be assessed through multiple methods, including (1) speaking with the care team to ensure that there are no concerns about capacity, (2) assessing the potential participant's mental status (for coma or agitation) via the Richmond Agitation Sedation Scale (RASS), and (3) performing a CAM-ICU to ensure that the patient is not delirious. If the patient is able to provide informed consent, study personnel will leave a copy of the signed consent form with the patient. If the patient is not able to make an informed decision the proxy will be approached for consent. As noted above, if consent is obtained from the proxy via telephone, we will mail the proxy an information sheet which serves as a copy of the consent.

Because this is a feasibility study that is gathering preliminary data, we need to gather basic data on the patients who are screened for this study; therefore, we are requesting a waiver of HIPAA authorization for screening/recruitment purposes only. A waiver of HIPAA authorization for recruitment/screening purposes will lessen burden on patients and families (since we only intend to enroll patients who meet basic inclusion criteria), and still allow us to accurately report the number and characteristics of screened patients.

For provider participation in this study, we will provide the appropriate information sheet (survey only, or survey and focus group) as this part of the study meets criteria for a waiver of documentation of consent. Research personnel will review the information sheet with the potential participant and answer any questions about the study.

5.3.1 Screening

The Yale-New Haven Hospital (YNHH) Joint Data Analytics Team (JDAT) will provide a list of medical intensive care unit (MICU) patients at the York Street campus who are age 65 and older and who have not opted out of research. Study personnel will review this list on a daily basis, as well as the MICU list with an extra check to ensure that the patient has not opted out of research, to screen for eligible patients. As noted in the prior section, because this is a feasibility study that is gathering preliminary data, we need to gather basic data on the patients who are screened for this study; therefore, we are requesting a waiver of HIPAA authorization for screening/recruitment purposes only. Study personnel will record basic demographic information and basic identifying information about the screened participants. The basic identifying information is necessary because we need to know if participants are screened more than once for this study, which is likely to happen since readmissions to the ICU are common.

A waiver of HIPAA authorization for recruitment/screening purposes will lessen burden on patients and families (since we only intend to enroll patients who meet basic inclusion criteria), and still allow us to accurately report the number and characteristics of screened patients.

5.3.2 Recruitment, Enrollment and Retention

Study personnel will review the JDAT-provided screening report and MICU roster (with an additional check to ensure that the patient has not opted out of research) each day and review the list for eligible patients by applying the inclusion and exclusion criteria detailed above in section 4.3.2. As outlined above in the Study Procedures (section 5.1), once an eligible patient is identified, a research nurse or research assistant will assess the patient for his/her ability to consent and participate in the study interventions by first assessing mental status via the Richmond Agitation-Sedation Scale (RASS). For patients who are too deeply sedated (RASS -2 to -5) or agitated (+2 to +5), as often occurs in the ICU due to severity of illness or the need for mechanical ventilation, a proxy will be approached for consent. Patients with an acceptable RASS score (-1, 0, or +1) will undergo an assessment of delirium using the Confusion Assessment Method for ICU (CAM-ICU). For patients who are delirious according to the CAM-ICU, as often occurs in the ICU due to severity of illness, a proxy will be approached for consent. Patients who have acceptable RASS scores and a negative CAM-ICU will be approached for enrollment. If study personnel have any concerns about the patient's capacity to consent once they begin speaking to the patient, they will administer the University of California San Diego Brief Assessment of Capacity to Consent (UBACC). If the patient is found to lack decisional capacity, a proxy will be approached for consent. Because we are studying a critically ill population, it is essential that we allow for consent by proxy because many of the participants may be too sick to consent themselves or participate in the baseline interview themselves.

All participants and/or proxies will be provided with a copy of the consent. In light of hospital visitation restrictions due to COVID-19, and considering that many proxies will not want to visit the hospital during the COVID-19 pandemic, we will allow for verbal consent by proxy. If verbal consent by proxy is obtained, we will log this in the REDCap database and mail the proxy an information sheet. If in-person consent is obtained, a copy of the consent will be provided at that time.

5.3.3 Study Visits

The study visits have been described in detail in section 5.1; as such, in this section we are providing the bulleted list of visits only. The estimated time for participant contact is listed next to each visit.

Patient participant study visits

- Baseline interview and provision of the portable amplifying device: 45 minutes
- Daily audit: 5 minutes/day.
- Hospital discharge interview: 45 minutes
- Follow-up phone interview approximately 30 days after discharge: 15 minutes

Provider participant study visits

- One 5-10 minute survey
- If the provider is recruited for and agrees to participate in a focus group, one additional study visit for the focus group: 1 hour on a separate date

5.4 Statistical Methods

5.4.1 Statistical Design, 5.4.2 Sample Size Considerations, and 5.4.3 Planned Analyses

SA1 Statistical Analysis: First, we will compile the data for each bundle component into an implementation report card. We will report the proportion of eligible patients receiving each

component, as well as the number of “doses” (for OT) and usage (for the hearing component) as outlined above. As a secondary analysis, we will evaluate delivery of the overall bundle. A feasibility threshold of 70% will be used for the individual bundle components, as well as the combined bundle (all 3 components).

The null hypothesis will be that <70% of patients will have received the bundle, with the alternative hypothesis that $\geq 70\%$ of the patients will have received the bundle. Analysis consists of a simple comparison of the post-delivery proportion of patients who have received the bundle. Using PASS 15 statistical software for a one-sided exact test based on normal approximation per the method of Fleiss, Levin and Palk (2003) with a one-sided alpha of 5%, we will have 100% power to detect a minimal proportion of 70%. To show robustness, if we lower power to 80%, with a sample of 65 we are powered to detect a proportion of 75% and with a sample of 55 we are powered to detect a minimal proportion of 78%. This implies our sample of 75 is more than adequate to detect meaningful rates at or above 70%.

SA2 Statistical Analysis: For each bundle component, we will define acceptability as a minimum average score of 7/10 on the Likert Scale (i.e., the minimum average over all Likert measurements for that component). As described in the grant, the pharmacists will rate acceptability at one timepoint (since the deprescribing intervention occurs once), whereas the nurses and occupational therapists will rate acceptability at multiple timepoints. For the latter two groups, we will calculate the overall mean count (i.e. the mean Likert score) over time, again using a minimum average of 7 as the smallest level of permissible acceptability.

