4.3.1 Number of Participants

We plan to enroll 80 patient participants (30 in the control group, and 50 in the intervention group). Of the providers, we plan to enroll 75 nurses and all of the occupational therapists and ICU pharmacists (approximately 3-5 in each group) who deliver the interventions.

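### The SA1 power statement is wrong as written: it claims 100% power at the null boundary, its n=65 and n=55 figures fail against a 70% null, and it uses 75 patients where 50 are planned

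*Combined protocol and SAP*

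**What the plan says.** All the sample-size reasoning for SA1 is in one paragraph of protocol section 5.4 (5.4.1 to 5.4.3 combined).

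- **Hypotheses:** "The null hypothesis will be that <70% of patients will have received the bundle", against an alternative of 70% or more, with one-sided alpha of 5%.
- **Main power claim:** "we will have 100% power to detect a minimal proportion of 70"%. The sentence gives no sample size.
- **First supporting figure, at 80% power:** "with a sample of 65 we are powered to detect a proportion of 75"%.
- **Second supporting figure, also at 80% power:** "with a sample of 55 we are powered to detect a minimal proportion of 78"%.
- **Conclusion drawn from these:** "This implies our sample of 75 is more than adequate to detect meaningful rates at or above 70"%.

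The preceding paragraph sets the 70% feasibility threshold for each component and for the combined bundle. It makes the combined bundle the secondary analysis: "As a secondary analysis, we will evaluate delivery of the overall bundle".

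On sample size, section 4.3.1 says "We plan to enroll 80 patient participants (30 in the control group, and 50 in the intervention group"). Section 4.2.1 limits the primary outcomes to people enrolled in the intervention phase.

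**The concern.** Three things look wrong. The alternative at which 100% power is claimed is the boundary of the null itself. Detecting rates 5 and 8 points above that boundary with 65 and 55 patients is far too optimistic for a one-sample proportion. And the conclusion rests on a sample that the current design does not have.

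This matters because the paragraph is the only sample-size justification for SA1, and it tells the reader the study can confirm rates at or above 70%. Section 2.2 says the results are meant to support a follow-on R01. A bundle that is in fact delivered to 75% or 80% of patients would usually fail to reject the null. With the present text beside it, that result would look like evidence of infeasibility from an adequately sized study.

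**Working it through.** **Inputs.** From section 5.4: p0 = 0.70, one-sided alpha 0.05, and the stated pairs (n=65, p1=0.75) and (n=55, p1=0.78). The 100% sentence gives no n, so I take 75 from the end of the paragraph (an assumption). From sections 4.2.1 and 4.3.1: at most 50 patients for SA1.

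**Formulas.** The plan describes its test as both exact and based on a normal approximation, so I did both.

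- Exact: find the smallest r with P(X ≥ r | n, 0.70) ≤ 0.05; power is P(X ≥ r | n, p1).
- Normal: power = Φ{[p1 − p0 − 1.645·√(p0(1−p0)/n)] / √(p1(1−p1)/n)}.

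**Step 1: the plan's own figures.** Normal approximation with the numbers put in:

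- n=75, p1=0.70: (0 − 0.0870)/0.0529 = −1.645, power 5.0%.
- n=65, p1=0.75: (0.05 − 0.0935)/0.0537 = −0.810, power 20.9%.
- n=55, p1=0.78: (0.08 − 0.1016)/0.0559 = −0.387, power 34.9%.

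| n | True rate | Stated power | Exact cutoff | Exact power | Normal approx. | True rate needed for 80% power (exact) |
|---|---|---|---|---|---|---|
| 75 | 70% | 100% | 60 | 3.5% | 5.0% | 82.9% |
| 65 | 75% | 80% | 52 | 21.8% | 20.9% | 83.1% |
| 55 | 78% | 80% | 45 | 30.9% | 34.9% | 84.9% |

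Continuity-corrected, arcsine, alternative-variance and two-sided versions do not recover the stated values either. The highest they give is 23.8% for n=65 and 41.6% for n=55.

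**Step 2: could another rule or null explain them?** A rule that simply requires an observed proportion of at least 70% passes 50.7% of the time at n=75 when the true rate is 70%. It passes 82.5% of the time for n=65 at 75% and 92.0% for n=55 at 78%. That does not give 100%, 80% and 80%, and its type I error is about 50%. Solving instead for the null that yields the stated power gives about 60.5% for n=65, about 62.6% for n=55 (both normal approximation), and about 45% or lower for the 100% claim at n=75 (exact power 99.6% at a null of 45%). These are three different nulls, and none is 70%.

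**Step 3: the sample the stated alternatives would need.** For 80% exact power against 70%, a true rate of 75% first reaches it at n=501 and holds it from 530. A true rate of 78% first reaches it at 193 and holds it from 208.

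**Step 4: the planned n of 50.** P(X ≥ 41 | 50, 0.70) = 4.0% and P(X ≥ 40 | 50, 0.70) = 7.9%, so the test rejects at 41 or more (82%).

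| True rate | 70% | 75% | 80% | 85% | 87% |
|---|---|---|---|---|---|
| Exact power, n=50 | 4.0% | 16.4% | 44.4% | 79.1% | 89.3% |

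The normal approximation gives 18%, 45% and 80% at 75%, 80% and 85%.

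**Step 5: fewer evaluable patients.** The plan writes "We will report the proportion of eligible patients receiving each" component, and under section 5.1 deprescribing takes place only at transfer to the floor. The evaluable number may therefore be below 50. The plan gives no figure, so I assume a range of 40 to 50: at n=45 the cutoff is 37 and power at 85% is 77%; at n=40 the cutoff is 34 and power at 85% is 61%.

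**Step 6: threshold against test.** An observed 35 to 40 of 50 meets a 70% threshold (0.70 × 50 = 35) but does not reject the null. The probability of landing there is 67% at a true rate of 75% and 53% at 80%.

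**The case against.** **It is a single-centre pilot with descriptive output.** No go/no-go decision is tied to rejecting the null, and the bundle test is labelled secondary. That is true, and a pilot need not claim power at all. But this plan does make a formal claim, with hypotheses and an alpha, and the claim is false. No other justification for SA1 is offered.

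**The software's null is not restated.** SA2 gives its null value as an input; the SA1 power sentence does not. So the implied nulls in step 2 are back-calculations and do not show what was run. This stands, and the finding is accordingly that the figures do not hold against the stated 70% null. The 100% claim is impossible against that null whatever was entered.

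**The bundle does have a stated test.** The less clear case is the three components, which carry the same 70% threshold with no hypothesis of their own. This is a fair refinement. For the bundle, though, the plan calls the analysis a simple comparison while also giving it a null and an alpha, so how its threshold is judged is unclear too.

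**The smaller denominators are speculative.** A patient who never transfers might be counted as not having received the bundle, in which case n stays at 50 and the delivery rate falls. The plan does not say which applies. Section 5.1.1 excludes days of deep sedation from amplifier use, but that removes days, not patients, so I give it no weight. The n=40 and n=45 figures are illustrations only.

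**Conclusion.** The concern holds in all three parts. Power at the null boundary is at most 5%, not 100%. The stated 80% figures are about 22% (n=65 at 75%) and 31% (n=55 at 78%) by the exact test, and 21% and 35% by the normal approximation. The sample of 75 contradicts the 50 intervention patients in the current text; the Protocol Revision History only shows that 75 was the former size of that group. The 75 nurses in section 4.3.1 cannot supply the number, because SA1 counts patients.

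The result rests on the stated null of 70% and one-sided 5%, on n=75 for the 100% claim, and on no loss from the 50. With 50 evaluable patients the smallest rate detectable with 80% power is about 85% (85.2% exact). This must be corrected, because every quantitative claim in the SA1 power statement is wrong.

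**What to change.** Delete the 100% claim and the figures for 65, 55 and 75. Suggested replacement:

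> Receipt of the bundle: one-sided exact binomial test of p ≤ 0.70 at 5%. With 50 evaluable patients the null is rejected at 41 or more of 50 (size 4.0%). Power is 16% at a true rate of 75%, 44% at 80%, 79% at 85% and 89% at 87%. Cutoff and power will be recomputed if fewer than 50 patients are evaluable.

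Writing the null as p ≤ 0.70 instead of below 0.70 leaves the test unchanged, because its size is set at the boundary. The n=45 and n=40 cases in step 5 can be added as examples.

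Also:

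- State who is in the denominator for each component and for the bundle, including patients who never transfer to the floor.
- Report each component and the bundle with an exact 95% confidence interval. If the bundle test is quoted, give the one-sided 95% lower bound as well: at 41/50 it is 70.7%, while the two-sided interval is 68.6% to 91.4% and would appear to contradict the rejection.
- State before analysis, separately for components and bundle, whether 70% is a descriptive benchmark on the observed proportion or is judged by the test. That choice is the investigators'.

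The cost is wording and a less favourable power statement; no extra patients are needed. If the bundle threshold is judged by the test, the observed bar rises from 35/50 to 41/50. If it stays descriptive, the bar does not change.
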